## **7.5 Safety**

Safety assessments will consist of monitoring and recording all adverse events, including serious adverse events, the regular monitoring of hematology (including glycosylated hemoglobin and coagulation parameters), blood chemistry (including fasting glucose, thyroid function tests), urine for microalbumin, regular monitoring of vital signs, gallbladder by MRI/CT ultrasound, will be recorded from study enrollment until study completion.

Patients with diabetes are to be instructed to check blood glucose levels via a fingerstick several times daily, particularly for the first few days of treatment.

### 7.5.1 Adverse events

An adverse event for the purposes of this protocol is the appearance of (or worsening of any pre-existing) undesirable sign(s), symptom(s), or medical condition(s) occurring after signing the informed consent even if the event is not considered to be related to the study drug(s). Please refer to the adverse event section of the protocol for the protocol-specific definitions of study drug and study treatment.

Adverse events will be assessed according to the Common Toxicity Criteria for Adverse Events [CTCAE] version 3.0. If CTCAE grading does not exist for an adverse event, the severity of mild, moderate, severe, and life-threatening, or grades 1 - 4, will be used. CTCAE grade 5 (death) will not be used in this study; rather, this information will be collected in the End of Treatment. Adverse event monitoring should be continued for at least 4 weeks following the last dose of study treatment.

Adverse events (but not serious adverse events) occurring before starting study treatment but after signing the informed consent form are recorded on the Medical History/Current Medical Conditions Electronic Case Report Form. Abnormal laboratory values or test results constitute adverse events only if they induce clinical signs or symptoms, are considered clinically significant or require therapy (e.g., any hematologic abnormality that requires transfusion or cytokine treatment); and should be recorded on the Adverse Events CRF under the signs, symptoms or diagnosis associated with them. In addition, isolated abnormal laboratory values that are considered clinically significant (e.g., cause study discontinuation or constitutes in and of itself a Serious Adverse Event) should be recorded on the Adverse Events CRF. SAEs occurring after signing the Informed Consent are recorded on the Adverse Event CRF.

The occurrence of adverse events should be sought by non-directive questioning of the patient at each visit during the study. Adverse events also may be detected when they are volunteered by the patient during or between visits or through physical examination, laboratory test, or other assessments. As far as possible, each adverse event should be evaluated to determine:

1. The severity grade (CTCAE grade 1-4)
2. Its relationship to each study drug (suspected/not suspected)
3. Its duration (start and end dates or if continuing at final exam)
4. Action taken (no action taken; study drug dosage adjusted/temporarily interrupted; study drug permanently discontinued due to this adverse event; concomitant medication taken; non-drug therapy given; hospitalization/prolonged hospitalization)
5. Whether it is serious, where a serious adverse event (SAE) is defined as one which:
  - Is fatal or life-threatening
  - Results in persistent or significant disability/incapacity
  - Constitutes a congenital anomaly/birth defect
  - Requires inpatient hospitalization or prolongation of existing hospitalization, unless hospitalization is for:
    - Routine treatment or monitoring of the studied indication, not associated with any deterioration in condition (specify what this includes)
    - Elective or pre-planned treatment for a pre-existing condition that is unrelated to the indication under study and has not worsened since signing the informed consent
    - Treatment on an emergency outpatient basis for an event not fulfilling any of the definitions of a SAE given above and not resulting in hospital admission

- Social reasons and respite care in the absence of any deterioration in the patient's general condition
- Is medically significant, i.e., defined as an event that jeopardizes the patient or may require medical or surgical intervention to prevent one of the outcomes listed above

Unlike routine safety assessments, SAEs are monitored continuously and have special reporting requirements; see protocol section on Serious Adverse Event reporting.

All adverse events should be treated appropriately. Such treatment may include changes in study drug treatment including possible interruption or discontinuation, starting or stopping concomitant treatments, changes in the frequency or nature of assessments, hospitalization, or any other medically required intervention. Once an adverse event is detected, it should be followed until its resolution, an assessment should be made at each visit (or more frequently, if necessary) of any changes in its severity, its suspected relationship to the study drug(s), any of the interventions required to treat it, and its outcome.

Information about common side effects already known about the investigational drug can be found in the [\[Investigator's Brochure\]](#) or will be communicated between IB updates in the form of Investigator Notifications. This information will be included in the patient informed consent and should be discussed with the patient during the study as needed.

### **7.5.2 Vital signs**

Body weight, body temperature, supine blood pressure, and supine pulse rate will be assessed. Height will be noted during the screening/baseline period.

### **7.5.3 Performance status**

SF36 quality of life form and Gastrointestinal Symptom Questionnaire will be used.

### **7.5.4 Laboratory evaluations**

Patients are to fast overnight for 8 hours prior to all biochemistry samples being taken. Blood samples are to be taken in the morning. Water is allowed during this time. Laboratory samples will be analyzed locally at Mayo Clinic. Albumin, alkaline phosphatase, total bilirubin, calcium, chloride, creatinine with calculated eGFR,  $\gamma$ -GT, fasting blood glucose, potassium, total protein, AST, ALT, sodium, urea/BUN. If the total bilirubin concentration is increased above 1.5 times the upper normal limit (UNL), total bilirubin should be differentiated into the direct and indirect reacting bilirubin.

#### **7.5.4.1 Abnormal liver function management:**

Perform within 72 hours of awareness of abnormal LFTs:

Perform liver-directed medical history and physical examination (i.e. assess occupational hazards, concomitant medications including OTC meds, intercurrent illness, etc)

Liver chemistry tests: ALT, AST, total bilirubin, (fractionate to direct/indirect bilirubin if total bilirubin is > 2.0x ULN), Alb, PT (INR), ALP, and GGT

Perform hepatitis screen: anti-HAV, IgM (to confirm acute hepatitis A), HbsAg, Anti-HBc, anti-HCV (if positive PCR viral load should be assessed), Anti-HEV, ANA antibodies, anti-smooth muscle anti-bodies, CMV, EBV

Perform abdominal ultrasound (liver and biliary tree)

Liver chemistry tests should be monitored every 3-4 days for LAR studies until resolution or return to baseline status.

For ALT or AST > 5x ULN and ≤ 8x ULN:

- Study medication should be temporarily interrupted and liver chemistry tests monitored **every 3-4 days** until resolution or return to baseline
- If resolution or return to baseline does not occur after 2 weeks, the patient should be discontinued.
- If ALT or AST returns to less than 5x ULN, study drug can be resumed and patient can continue study per protocol
- If ALT or AST rises above 5x ULN anytime after study drug is resumed, then study drug should be discontinued immediately.

Resolution return to baseline does not occur after two weeks the patient should be discontinued

If ALT or AST rises about 5X ULN anytime after study drugs resumed and study drug to be discontinued immediately

Study medication should be discontinued immediately if any of the discontinuation criteria below are met: (see appendix 4)

ALT or AST > 3x ULN and Total Bilirubin ≥ 2x ULN and ALP < 2x ULN

ALT or AST > 5x ULN and ≤ 8x ULN persistent for more than 2 weeks

ALT or AST > 8x ULN

Re-challenge of study medication is prohibited once discontinuation criteria are met.

#### **7.5.4.2 Thyroid function tests**

Free T4 and TSH will be assessed prior to enrollment and at 6 months.

#### **7.5.4.3 Urine tests:**

Serial spot urine microalbumin measurements will be followed.

#### **7.5.4.4 Hormone assessments**

GH, IGF-1 and prolactin (PRL), will not be assessed.

#### **7.5.4.5 Urinalysis**

Specific gravity, pH, glucose, protein, bilirubin, ketones, leukocytes and blood will be assessed.

#### **7.5.4.6 Pregnancy test**

Study drug treatment should be withdrawn in the event of pregnancy. To ensure patient safety each pregnancy must also be reported to Novartis within 24 hours of learning of its occurrence. The pregnancy should be followed up to determine outcome, including spontaneous or voluntary termination, details of birth, and the presence or absence of any birth defects, congenital abnormalities or maternal and newborn complications. Any SAE experienced during pregnancy must be reported on the SAE Report Form.

#### 7.5.4.7 Gallbladder Imaging

The gallbladder will be imaged at baseline (by MRI or CT) and repeated 6 monthly until the end of study. Patients with a history of symptomatic cholelithiasis are excluded from participating in the study.

#### 7.5.4.8 Electrocardiogram (ECG)

A 12-lead electrocardiogram (ECG) and rhythm strip will be performed at baseline and 30 minutes after the first dose one half and 3 monthly for the first year and every 6 months in year 2. Repeat ECG on the 21st day after the injection, then every 3 months thereafter.

If a clinically significant abnormality is detected, the electrocardiogram will be repeated at the discretion of the Investigator until the abnormality has been resolved. *A cardiology consultation must be sought as soon as practical but within 7 days of the initial abnormal ECG and the cardiologist must re-evaluate the ECG (this can be done by the central cardiologist). An echocardiogram may also be required.*

- If a QTcF > 480msec is NOT confirmed, no further action needs to be taken.
- If a QTcF > 480msec is confirmed, a cardiologist must perform a thorough examination (such as reviewing baseline ECG, concurrent medications and performing a cardiovascular examination, including at least a cardiac auscultation) to assess the patient for cardiovascular risk factors.

#### 7.6 Pharmacokinetics

Blood levels of pasireotide will be done in this protocol.

### 8 Other Safety Considerations:

The potential risks to patients should be limited to study drug use as no specific change in diet and pharmacologic treatment will be introduced throughout the study, unless deemed clinically appropriate to control blood pressure or limit the signs of renal or liver dysfunction. Antihypertensive treatment will be adjusted in order to maintain a target systolic/diastolic blood pressure <130/80 mm Hg. Blood glucose levels will be carefully monitored during the study and antidiabetic therapy adjusted if indicated. Other medications necessary for medical management or symptomatic treatment, including analgesics, antiemetics, antidiarrheals, and thyroxine, will be administered as clinically indicated. Claustrophobic patients will be provided a standing order of oral lorazepam 1mg 45 minutes before their MRI according to the standard Mayo Radiology Department Protocol.

The NCI common toxicity criteria 3.0 will be used to classify adverse events (both patient and event counts) by organ system (neuro, GI, etc.), individually, by severity and, for each severity, by investigator-assessed relationship to study drug. Fisher's exact test will be used to compare treatment groups (placebo, SOM230) regarding adverse events during year 1. Patients who received at least one dose of the randomized study drug will be included. Adverse events in years 2 and 3 (all subjects on SOM230) will be reported separately. A data safety committee will meet **every six months** (comprising of two physicians; [REDACTED]). The committee will meet with the study coordinator and PI and review safety labs and monitoring and study conduct.

### 8.1.1.1 Adverse events

Information about all adverse events, whether volunteered by the subject, discovered by investigator questioning, or detected through physical examination, laboratory test or other means, will be collected and recorded and followed as appropriate.

An adverse event is the appearance or worsening of any undesirable sign, symptom, or medical condition occurring after starting the study drug even if the event is not considered to be related to study drug. Medical conditions / diseases present before starting the study drug are only considered AEs if they worsen after starting the study drug. Abnormal laboratory values or test results constitute adverse events only if they induce clinical signs or symptoms, are considered clinically significant, or require therapy.

The occurrence of adverse events should be sought by non-directive questioning of the patient at each visit during the study. Adverse events also may be detected when they are volunteered by the patient during or between visits or through physical examination, laboratory test, or other assessments. As far as possible, each adverse event should be evaluated to determine:

- the severity grade (mild, moderate, severe) or (grade 1-4)
- its relationship to the study drug(s) (suspected/not suspected)
- its duration (start and end dates or if continuing at final exam)
- action taken (no action taken; study drug dosage adjusted/temporarily interrupted; study drug permanently discontinued due to this adverse event; concomitant medication taken; non-drug therapy given; hospitalization/prolonged hospitalization)
- whether it constitutes a serious adverse event (SAE)

All adverse events should be treated appropriately. Such treatment may include changes in study drug treatment including possible interruption or discontinuation, starting or stopping concomitant treatments, changes in the frequency or nature of assessments, hospitalization, or any other medically required intervention. Once an adverse event is detected, it should be followed until its resolution, and assessment should be made at each visit (or more frequently, if necessary) of any changes in severity, the suspected relationship to the study drug, the interventions required to treat it, and the outcome.

Information about common side effects already known about the investigational drug can be found in the [\[Investigators' Brochure\]](#) or will be communicated between IB updates in the form of Investigator Notifications. This information will be included in the patient informed consent and should be discussed with the patient during the study as needed.

#### 8.1.1.1 Serious adverse events

Information about all serious adverse events will be collected and recorded. To ensure patient safety each serious adverse event must also be reported to Novartis within 24 hours of learning of its occurrence. A serious adverse event is an undesirable sign, symptom or medical condition which:

- is fatal or life-threatening
- results in persistent or significant disability/incapacity

- constitutes a congenital anomaly/birth defect
- requires inpatient hospitalization or prolongation of existing hospitalization, unless hospitalization is for:
  - routine treatment or monitoring of the studied indication, not associated with any deterioration in condition (specify what this includes)
  - elective or pre-planned treatment for a pre-existing condition that is unrelated to the indication under study and has not worsened since the start of study drug
  - treatment on an emergency outpatient basis for an event not fulfilling any of the definitions of a SAE given above and not resulting in hospital admission
  - social reasons and respite care in the absence of any deterioration in the patient's general condition
- is medically significant, i.e., defined as an event that jeopardizes the patient or may require medical or surgical intervention to prevent one of the outcomes listed above

### **8.1.2 Novartis instructions for rapid notification of serious adverse events**

The principal investigator has the obligation to report all serious adverse events to the FDA, IRB, and Novartis Pharmaceuticals Integrated Medical Safety (IMS).

All events reported to the FDA by the investigator are to be filed utilizing the Form FDA 3500A (MedWatch Form).

All events must be reported, by **FAX** (██████████), to Novartis Pharmaceuticals IMS Department within 24 hours of learning of its occurrence. This includes serious, related, labeled (expected) and serious, related, unlabeled (unexpected) adverse experiences. All deaths during treatment or within 30 days following completion of active protocol therapy must be reported within 1 working day.

Any serious adverse event occurring after the patient has provided informed consent and until 4 weeks after the patient has stopped study participation must be reported. This includes the period in which the study protocol interferes with the standard medical treatment given to a patient (e.g. treatment withdrawal during washout period, change in treatment to a fixed dose of concomitant medication).

Serious adverse events occurring more than 4 weeks after study discontinuation need only be reported if a relationship to the Novartis study drug (or therapy) is suspected.

For Comparator Drugs/Secondary Suspects (Concomitant Medications), all serious adverse experiences will be forwarded to the product manufacturer by the investigator.

#### **8.1.2.1 Pregnancies**

Any pregnancy that occurs during study participation should be reported. To ensure patient safety each pregnancy must also be reported to Novartis within 24 hours of learning of its occurrence. The pregnancy should be followed up to determine outcome, including spontaneous or voluntary termination, details of birth, and the presence or absence of any birth defects, congenital abnormalities or maternal and newborn complications.

## 9 Protocol amendments, or changes in study conduct

Any change or addition (excluding administrative) to this protocol requires a written protocol amendment that must be reviewed by Novartis and the investigator before implementation. Amendments significantly affecting the safety of subjects, the scope of the investigation or the scientific quality of the study require additional approval by the IRB at each study center. A copy of the written approval of the IRB must be provided to Novartis. Examples of amendments requiring such approval are:

1. increases in drug dose or duration of exposure of subjects,
2. significant changes in the study design (e.g. addition or deletion of a control group),
3. increases in the number of invasive procedures,
4. addition or deletions of a test procedure required for monitoring of safety.

These requirements for approval should in no way prevent any immediate action from being taken by the investigator or by Novartis in the interests of preserving the safety of all patients included in the trial. If an immediate change to the protocol is felt to be necessary by the investigator and is implemented for safety reasons Novartis must be notified and the IRB at the center must be informed immediately. Amendments affecting only administrative aspects of the study do not require formal protocol amendments or IRB approval but the IRB must be kept informed of such administrative changes. Examples of administrative changes not requiring formal protocol amendments and IRB approval include:

1. changes in the staff used to monitor trials,
2. minor changes in the packaging or labeling of study drug.

## 10 Data management

### 10.1 Data collection

Every patient will have a study folder containing source documents, report forms; original signed consent, and stored in a locked area in the study coordinator's office [REDACTED] [REDACTED] Serial data entry recording the information required by the protocol from initial and subsequent visits will be entered on SDMS spreadsheets, and maintained on a password protected Nephrology secure server. Statistical methods

### 10.2 Statistical methods

Demographics and laboratory data will be plotted (e.g. box plots) and summarized by treatment group. Frequency distributions will be used to describe categorical values and basic summary statistics (mean, standard deviation, median, and inter-quartile range) used to describe continuous values. All tests will be two-sided with alpha level 0.05. For quantitative endpoints (e.g. change in kidney and liver volumes, renal function, and SF-36 scales) the two-group independent samples t-test will be used to test for an effect of treatment. Should the assumptions of normality and equality of variances be untenable, we will consider a data transformation or use of the Wilcoxon rank sum test. Both point estimates (mean) and 95% confidence intervals will be used to summarize treatment effects. For qualitative endpoints (e.g. presence or absence of response) we will compare treatment groups using the chi-square or Fisher's exact test as appropriate.

**Efficacy (Liver & kidney):** The primary analysis of treatment efficacy will follow intent-to-treat principles, attempting to include all randomized patients. For the primary endpoint (change in

liver volume) we will not be able to include anyone without a 12 month MRI (kidney volumes will be handled in the same way). For the “response” endpoints, those without a 12 month MRI will be included in the analysis as non-responders. Secondary analysis – Efficacy (QOL): We will have up to 5 longitudinal assessments of QOL for each patient. Repeated measures analysis of variance will be used to compare mean QOL profiles over time between treatment groups. Also, within patient rates of change or slopes in QOL measures will be estimated (using simple linear regression) and compared between groups using the two-sample t-test.

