## **4 Study design**

This study will be conducted over 3 years as a randomized, double-blind control, clinical trial through year 1, followed by an open-label extension phase for the subsequent 2 years. Screening and randomization visits will take place at Mayo Clinic and patients will then be followed by Mayo Clinic for three years. We will monitor the patients with blood and urine tests on days 22, 29, 50, 57 and 89 and then at Months 6, 9, 12, 15, 18, 24, 27, 30, 33 and 36. Follow up visits will occur at one and three months post last dose of study drug. For patients who received placebo during year one, the labs on days 22, 29, 50, 27 and 85 will be repeated as these are safety labs. All patients will be required to undergo MRI or CT scan imaging at the baseline, 12 month (end

of year 1) and 36 month (end of year 3) visits to fulfill the primary study endpoints. Safety monitoring with ECG, Hemoglobin A1C, liver function and glucose testing will be performed locally at the study sub-sites and monitored centrally by study staff at Mayo Clinic.

Patients will be recruited during visits to the Department of Nephrology and Hypertension

Patients who had participated in previous studies will also be contacted as long as they meet all eligibility criteria. We will also recruit through [clinicaltrials.gov](http://clinicaltrials.gov) ( <http://clinicaltrials.gov> ), Mayo Clinic Trials website ( <http://clinicaltrials.mayo.edu/> ) and PKD foundation clinical trials ( <http://www.pkdcure.org/Research/ClinicalTrials/ActiveRecruiting.aspx> ) listed on the web . Patients who contact the study coordinator will be given information regarding the study and participation. The study coordinator will screen those interested and proceed with the study design for all patients who would like to participate.

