#### 6.2 Treatment arms

There will be stratified randomization for PLD patients with ADPLD and ADPKD (see Table 5):

All participants who receive the placebo during year one will be given the option to continue on study to receive active study drug for years two and three. Thus, all participants will be receiving SOM230 years two and three.

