**Table 5 Stratified randomization**

Disease Group	SOM230	Placebo
ADPLD	8	4
ADPKD	24	12
Total	32	16

The initial assessment will be derived on a clinical basis as some individuals with ADPLD also may have kidney cysts.

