## 6.5 Pasireotide LAR dose adjustment

We will use the oncology dosing (including NETs) as already described above, pasireotide LAR at 60 mg every 28 days being the recommended starting dose for oncological indications. If tolerability issues occur, the treatment dose may be reduced to pasireotide LAR at 40 mg with next scheduled injection. Patients requiring a dose reduction can return to the higher dose once the tolerability issue is resolved. However, patients not able to tolerate the minimum pasireotide LAR dose of 20 mg are recommended to be discontinued from study.

All dose changes must be recorded on the Dosage Administration Record CRF. Table 7 outlines the dose reduction steps for pasireotide.

Emergency un-blinding will be done at the discretion of the Principal Investigator [REDACTED] in cases where she feels it is necessary for the safety of the patient.

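### The primary t-test uses neither the randomisation stratum nor baseline liver volume, which may cost some precision; separately, the withdrawal wording must be reconciled with the month-12 scan required of all patients.

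*Combined protocol and SAP*

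**What the plan says.** **Design.** Section 6.2 states: "There will be stratified randomization for PLD patients with ADPLD and ADPKD". Table 5 plans 8 and 4 patients with ADPLD and 24 and 12 with ADPKD (SOM230 and placebo). Its footnote adds: "The initial assessment will be derived on a clinical basis as some individuals with ADPLD also may have kidney cysts". The first classification may therefore be revised later.

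**Analysis.** For quantitative endpoints, including change in liver volume, section 10.2 says "the two-group independent samples t-test will be used to test for an effect of treatment". If normality or equal variances fail, "we will consider a data transformation or use of the Wilcoxon rank sum test". Neither option uses the stratum or baseline volume, and no order of preference is given. Section 3.1 makes both absolute and percent change to month 12 primary objectives.

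**Scans and withdrawal.** Section 4 says "All patients will be required to undergo MRI or CT scan imaging at the baseline, 12 month" (and month 36). Sections 6.5 and 6.6 say "patients not able to tolerate the minimum pasireotide LAR dose of 20 mg are recommended to be discontinued from study". Section 6.8 pairs stopping drug for a significant safety risk with withdrawal from the trial, and section 6.9 asks withdrawn patients for an Early Termination Visit. Table 7 speaks only of discontinuing study treatment. Section 10.2 follows intent-to-treat principles, but for the primary endpoint "we will not be able to include anyone without a 12 month MRI". In the response analysis, "those without a 12 month MRI will be included in the analysis as non-responders".

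**The concern.** A trial of 48 patients has little precision to spare. It stratifies on a factor thought to matter and measures the baseline of its own endpoint, then uses neither. The unordered fallback leaves a choice open until the data have been seen.

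On withdrawal, a patient removed from the study cannot also have the scan that section 4 requires of everyone. Stopping drug and leaving the study are not kept apart. So it is unclear whether the primary mean change describes everyone randomised or mainly those who stayed on drug. The result has consequences: under section 6.10 the open-label extension ends if year 1 shows no efficacy.

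**Working it through.** **1. The plan's own figure.** Section 10.2 states 80% power for a 7-point difference with 15 placebo and 30 SOM230 patients, two-sided alpha 0.05. The noncentrality is 7 / (SD × √(1/15 + 1/30)), with 43 degrees of freedom.

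- SD 3, the only SD in the power paragraph: power is near 100%, so the stated 80% is not reproduced.
- SD 7.00, 7.58 and 8.35 (sections 1.5.2.2 and 1.3): 87.1%, 81.4% and 73.6%.
- Exactly 80% needs SD 7.72. The noncentrality is then 7 / (7.72 × 0.316) = 2.87, and the 95% CI half-width is 4.93 points.

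SD 7.72 is used below as an assumption consistent with the plan's 80%.

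**2. Validity of the t-test.** Simulation used 48 patients split as in Table 5 and SD 7.72, with 8,000 trials per setting. For ADPKD/ADPLD mean differences of 0, 3, 5 and 8 points, type I error of the t-test was 0.053, 0.047, 0.043 and 0.026. ANCOVA stayed between 0.049 and 0.052.

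**3. Power of the ANCOVA.** The residual SD is 7.72 × √(1 − R²), with 41 degrees of freedom. Counting only the lost degrees of freedom is too kind, because baseline volume is not stratified and can differ between arms by chance. The last column includes that imbalance, by simulation.

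| R² (assumed) | t-test | ANCOVA, degrees of freedom only | ANCOVA with chance imbalance |
|---|---|---|---|
| 0 | 80% | 79.9% | about 79% |
| 0.05 | 80% | 81.9% | about 81% |
| 0.10 | 80% | 83.9% | about 83% |
| 0.20 | 80% | 87.9% | about 87% |

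Break-even is near R² = 0.025. With a quarter of patients having ADPLD (12 of 48), the stratum alone gives R² = 0.25 × 0.75 × difference² / 7.72². That is 0.013 for a 2-point difference, below break-even, and 0.050 for 4 points. Any useful gain must come from baseline volume or from a strong stratum effect.

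**4. Rank fallback.** Power of the van Elteren test against the plain Wilcoxon test, by simulation, was 79.1% against 80.1% (no stratum difference), 79.7% against 80.2% (2 points) and 81.8% against 81.1% (4 points). Stratifying the rank test helps only when the stratum is clearly prognostic.

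**5. Patients who stop drug.** Suppose a fraction of the SOM230 arm stops drug and keeps none of a 7-point benefit. Leaving them out overstates the as-randomised effect by 7 × that fraction:

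- planned loss of 2 of 32 (section 10.2): 7 × 2/32 = 0.44 points;
- the 15% ceiling in section 6.10: 7 × 0.15 = 1.05 points.

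If half the benefit is kept, these halve to 0.22 and about 0.53. Keeping such patients dilutes the effect. t-test power at SD 7.72:

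| Off drug | Kept, no benefit (16/32) | Kept, half benefit (16/32) | Dropped |
|---|---|---|---|
| 2 of 32 | 76.5% | 79.9% | 81.7% (16/30) |
| 15% | 66.4% | 75.9% | 80.1% (16/27) |

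**6. Early scans.** If untreated growth of 5% a year (section 10.2) is linear, which is an assumption, a scan at month 4 shows 5 × 4/12 = 1.7 points of growth rather than 5.

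**The case against.** The strongest reply is that the t-test is pre-specified and sound, and that adjustment is a preference. Percent change already divides by baseline, and nothing in the documents shows that stratum or baseline volume predicts it. Below R² of about 0.025 the ANCOVA is slightly worse. This stands, and it limits the first point to a possible gain with a small known cost. It has less force for absolute change, which is also a primary objective and is not scaled by baseline.

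A reader might infer that ignoring the stratum inflates type I error. Step 2 shows the opposite. A reader might equally infer that adjustment is free, which step 3 does not support.

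On withdrawal, section 10.2 is open that patients without a month-12 scan are left out, and it counts them as non-responders in the response analysis. Its rule depends on having the scan, not on being on drug, so an off-drug patient scanned at month 12 is already included. A reader might infer that an early-termination scan could serve as the endpoint, because Table 8 puts Early Termination in the month-36 column and the imaging row seems to have a mark there. The layout of that table in the text is too damaged to rely on, and the 12-month wording of the endpoint already excludes such a scan. What stands is that nothing says patients who stop drug return at month 12, and several sections suggest they leave the study.

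**Conclusion.** The concern holds as a modest improvement, not as an error of validity. The primary test omits a stratum used in randomisation and a baseline measured in everyone. At SD 7.72, using them changes power by between about −1 and +7 points for R² from 0 to 0.20. Both the SD and the R² range are assumptions.

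The conflict in the withdrawal wording is real but secondary, because the exclusion is disclosed and affects only the mean-change analyses. The worst-case overstatement is 0.44 points at the planned loss and about 1.05 at 15%, against a CI half-width of 4.93. It is about zero if losses are balanced and unrelated to outcome. Removing this risk costs power, as step 5 shows. That is the price of the intent-to-treat estimate that section 10.2 sets out to give.

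**What to change.** 1. Make the primary analysis an ANCOVA of 12-month percent change in liver volume on treatment, disease stratum as randomised and baseline liver volume. Use the same model for absolute change. Keep the t-test as a sensitivity analysis.
2. Fix the fallback order in advance: if normality fails, first fit the same model to log(month-12 volume / baseline volume). A rank test is optional.
3. Reconcile sections 4, 6.5, 6.6, 6.8, 6.9 and 10.2 and Table 7. Make clear that patients who stop drug without withdrawing consent still have the month-12 scan (MRI or CT, as section 4 allows) and are analysed as randomised. The rules for stopping drug are not touched.
4. State that an early-termination scan is not a 12-month scan and does not enter the primary endpoint.

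**Cost.** SAP wording and a short amendment. Items 1 and 2 cost about 1 power point if the covariates explain nothing. Item 3 adds no scan beyond those section 4 requires, but off-drug patients must be retained to month 12 and the dilution in step 5 accepted.
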